4.2 Subjects completion/withdrawal from the trial

4.2.1 Completion of studies

Patients met inclusion/exclusion criteria and signed ICF until completion of 1 year of follow-up.

4.2.2 Termination of treatment

Patients have the right to withdraw from the study at any time without any reason and their subsequent treatment will not be affected in any way by this. Subjects should discontinue study treatment if any of the following occurs:

- (1) Significant protocol violations (including poor adherence, failure to meet inclusion criteria or meeting exclusion criteria for enrollment, etc.) as confirmed by the principal investigator (PI);
- (2) Serious procedure-related complications during percutaneous LAAO;
- (3) Patients who are no longer suitable for continued participation in the study due to adverse events for patient safety reasons;
- (4) The patient refuses to participate or refuses to continue to participate in this study;
- (5) Pregnancy.

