	
3. Follow-up: Baseline patient data will be collected prior to the first procedure. Follow-up visits will occur within 7 days post-LAAO or at discharge, and at 1 month (i.e., time of the second procedure), 3 months, and 12 months post-procedure. Follow-up will focus on device endothelialization at 12 months, recurrence of atrial fibrillation, and occurrence of related complications.
 
Postoperative Medication Management Strategy:
 
Patients will receive anticoagulation therapy for 1 month following LAAO with the WATCHMAN FLX device. If no thrombosis or significant residual flow is detected, catheter ablation for atrial fibrillation will be performed. After the ablation procedure, anticoagulation therapy will be continued for an additional 2 months. Antiarrhythmic drugs (AADs) may be used within 90 days post-ablation in accordance with AF management guidelines.

Primary endpoint	The success rate of complete left atrial appendage (LAA) closure within 12 months following LAAO with the WATCHMAN FLX device, as assessed by LAA computed tomography angiography (CTA).
Secondary endpoint	
Safety Endpoints:
 
Incidence of procedure-related complications and adverse events within 30 days after LAAO and radiofrequency ablation, including rates of pericardial effusion, access site complications, vascular complications, and infections. The incidence of procedure-related complications and adverse events within 12 months following LAAO and radiofrequency ablation will be evaluated. These include major bleeding events (defined as those requiring blood transfusion or surgical intervention), cardiac tamponade, systemic embolism (including ischemic stroke and other embolic events), device-related thrombosis (DRT), new or enlarged peri-device leak (PDL, defined as >5 mm), acute postoperative left heart failure, and rehospitalization.
 
Efficacy Endpoints:
 
 1. Treatment success rate within 3 months after radiofrequency ablation (Early recurrence): No recurrence of atrial arrhythmias ≥ 30 seconds. 2. Treatment success rate between 4 to 12 months after ablation (Late recurrence): No recurrence of atrial arrhythmias ≥ 30 seconds during this period. 3. Incidence of stroke within 12 months following LAAO: No occurrence of stroke.

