4.2.3 Exit trial

This subject will be withdrawn from the trial for the following reasons:

- (1) Death;
- (2) Lost visits;
- (3) Withdrawal of ICF.

Subjects who terminate or withdraw early from the study are required to be contacted by research center staff making every effort to determine the reason for early termination or withdrawal and the presence of any adverse events. Subjects who terminate or withdraw early from the study need to be thoroughly evaluated at the final visit and documented as thoroughly as possible. The reason for early termination or withdrawal from the study, the date, and the final evaluation must be documented in the study materials.

5. Data management and statistical analysis plan, information

confidentiality plan

A clinical trial summary report will be written based on the statistical analysis report. The investigator maintains all study materials, including confirmation of all participating subjects (able to effectively verify different recorded information, such as original hospital records), all original informed consent forms signed by the patient, and all case observation forms. The investigator will keep the information about the subjects closely until its final destruction, during which time it will not continue to use or disclose the information.

Evaluation of the Safety and Efficacy of Catheter Ablation Following Left Atrial Appendage Occlusion Using the WATCHMAN FLX Device
However, in the rare cases listed below, the investigator will continue to use or disclose information about a subject even if the subject has withdrawn from the study or the study has been completed. These situations include: when the removal of the subject's information would affect the scientific validity of the results of the study or the evaluation of the safety of the data; to provide some limited information for research, teaching, or other activities (this information will not include names, identification numbers, or other personally identifiable information); when government regulators need to oversee the study, they will ask to see all of the information about the study, which will also include information about the subject's information about their participation in the study at that time.

6. Statistical analysis

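### Sections 4.2.2 and 4.2.3 do not cleanly separate stopping study treatment from leaving the study, and nothing secures follow-up to the 12-month CT once treatment stops

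*Protocol*

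**What the plan says.** Section 4.2 of the protocol covers both completion of and withdrawal from the trial.

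- **Section 4.2.2** is headed as termination of treatment. It opens with a statement about the study: "Patients have the right to withdraw from the study at any time without any reason". Its operative sentence is about treatment: "Subjects should discontinue study treatment if any of the following occurs". Five grounds follow. Ground (2) is "Serious procedure-related complications during percutaneous LAAO". Ground (3) differs in kind, because it speaks of the study and not of treatment: "Patients who are no longer suitable for continued participation in the study due to adverse events for patient safety reasons". The others are major protocol deviations, such as poor adherence or an eligibility failure, once the principal investigator has confirmed them (1), the patient's refusal (4) and pregnancy (5).
- **Section 4.2.3** is headed as exit from the trial. It says "This subject will be withdrawn from the trial for the following reasons" and lists three: death, lost visits and withdrawal of consent. Its closing paragraph adds: "Subjects who terminate or withdraw early from the study need to be thoroughly evaluated at the final visit".
- **Section 4.1**, the visit schedule, marks adverse events at every visit and CT as an actively collected item at Visit 7 (one year).
- **Section 8.5** follows adverse events until they resolve or the patient is stable.
- **The Summary**, under the safety endpoints, promises a one-year horizon: "The incidence of procedure-related complications and adverse events within 12 months following LAAO and radiofrequency ablation will be evaluated".

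**The concern.** Whether a patient who stops treatment is still observed is a rule of conduct, and a site needs to find it in the protocol. Here the headings say one thing and parts of the wording another. Ground (3) ends participation in the study, inside a list that is meant to end treatment only. The final-visit sentence in 4.2.3 speaks of subjects who terminate, a word that matches the heading of 4.2.2 and none of the three exit reasons in 4.2.3. A site could reasonably conclude that a patient stopped under 4.2.2 has a final visit and is then closed.

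Grounds (2) and (3) select on complications and adverse events. If such patients are closed out, missing data depend on the outcomes being counted: new strokes, bleeds, device thrombi and leaks up to month 12, and possibly the closure result itself. The primary test is single-arm against a fixed 74.3%, so there is no control group in which the same loss would offset the bias. An analysis plan can choose a denominator or an imputation rule, but it cannot recover a CT or an event that was never collected.

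**Working it through.** **Step 1. Ground by ground**

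| 4.2.2 ground | Literal effect | In the 4.2.3 exit list? |
|---|---|---|
| (1) Protocol violation, poor adherence | stops treatment | no |
| (2) Serious LAAO complication | stops treatment | no |
| (3) Adverse event | worded as ending study participation | no |
| (4) Refusal | worded as ending study participation | overlaps with withdrawal of consent |
| (5) Pregnancy | stops treatment | no |

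Ground (3) is the direct conflict: participation ends under 4.2.2 for a reason that 4.2.3 does not recognise as exit. For (1), (2) and (5), close-out is only an inference, prompted by the shared word for termination and the final-visit sentence.

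**Step 2. Does another passage settle it?** The schedule in 4.1 lists what is done at Visits 6 and 7, not who still attends after stopping treatment. Section 4.2.1 defines completion as one year of follow-up but does not say that a 4.2.2 patient continues to that point. Section 8.5 follows events already recorded; it does not provide for detecting new ones or for the CT. None of the three secures the 12-month data.

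**Step 3. Size, worst case**

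Inputs from section 6.1: P0 = 0.743, one-sided α = 0.05, N = 210. The planned loss allowance reproduces as 200 × 1.05 = 210, that is, 10 patients. The documents give no count of patients stopped under 4.2.2.

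Assumptions made here: k patients are closed out before the CT; all k would have been non-closures; only the m = 210 − k patients with a CT are analysed; exact binomial test.

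*Observed rate.* Start from 156/210 = 74.3%, which is the target, and remove k non-closures: rate = 156/(210 − k).

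*False-success chance.* True closure in all 210 is 74.3%, so the rate among those with a CT is 0.743 × 210/m. The success threshold r is the smallest count with P(X ≥ r | m, 0.743) ≤ 0.05. The false-success chance is P(X ≥ r | m, 0.743 × 210/m).

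| k | m | 156/m | r | Rate among those with CT | False-success chance |
|---|---|---|---|---|---|
| 0 | 210 | 74.3% | 167 | 74.3% | 4.7% |
| 4 | 206 | 75.7% | 164 | 75.7% | 11% |
| 8 | 202 | 77.2% | 161 | 77.2% | 23% |
| 10 | 200 | 78.0% | 160 | 78.0% | 28% |

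For k = 4, for example: 0.743 × 210/206 = 0.757, and P(X ≥ 164 | 206, 0.757) = 0.11.

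**The case against.** A reader might infer from these sections that a patient with an LAAO complication, or one who adheres poorly, must leave the study and so loses the 12-month CT and all safety follow-up. The documents do not support that. The operative sentence of 4.2.2 stops treatment, neither reason is in the exit list of 4.2.3, and the final-visit sentence is addressed to those who leave the study. Nor are safety data lost entirely: recorded events are followed under 8.5, and 4.2.3 asks centre staff to make every effort to establish adverse events in anyone who leaves early. What could be missed is new events and the CT.

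It is also too strong to say that after implantation nothing remains to stop but observation. Ablation, anticoagulation after each procedure and optional antiarrhythmic drugs are all part of the regimen.

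The arithmetic has limits. Nothing in the documents links a procedural complication to incomplete closure, so counting every lost patient as a non-closure is an extreme. The shift alone would not turn the illustrated result into a success: 156 of 202 gives an exact one-sided p of 0.19, and success would need 161 of 202 (79.7%).

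All of that stands. It does not remove the conflict in ground (3), the ambiguous reach of the final visit, or the absence of any statement that follow-up continues.

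**Conclusion.** The point holds as a conflict and a gap in the conduct rules, not as a stated rule that removes the worst-faring patients. Sections 4.2.2 and 4.2.3 must be reconciled. As written, they allow a site to close out patients for reasons related to outcome, and no other passage secures the 12-month CT or the detection of new safety events.

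The size is unknown. Under the worst-case assumptions above, 4 to 8 lost patients of 210 (2–4%) raise an observed 74.3% to 75.7–77.2% and the false-success chance from about 5% to 11–23%. Both effects shrink if some lost patients would have had complete closure, or if the analysis counts a missing CT as failure. That second safeguard would protect the primary test only; it would not restore missing safety events. The point does not depend on how the sample size was derived.

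**What to change.** Reconcile the two sections with a short clarification stating that:

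- stopping or not receiving a study procedure under 4.2.2 does not by itself end participation;
- any patient with an LAAO attempt who has not withdrawn consent continues Visits 6 and 7 and adverse-event collection, with the 12-month CT where a device is in place;
- the final visit applies only to the exit reasons already listed in 4.2.3.

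Align the wording of ground (3) with that distinction between treatment and participation. Leave the clinical grounds for stopping treatment unchanged; the 4.2.3 exit list needs no change either.

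The cost is one amendment paragraph, which under section 7.1 needs ethics committee approval before use. A few patients would complete visits that are already planned, and the reported closure and complication rates may be slightly less favourable. The change should be made promptly, because data missed in the meantime cannot be recovered.

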4.2.3 Exit trial

This subject will be withdrawn from the trial for the following reasons:

- (1) Death;
- (2) Lost visits;
- (3) Withdrawal of ICF.

Subjects who terminate or withdraw early from the study are required to be contacted by research center staff making every effort to determine the reason for early termination or withdrawal and the presence of any adverse events. Subjects who terminate or withdraw early from the study need to be thoroughly evaluated at the final visit and documented as thoroughly as possible. The reason for early termination or withdrawal from the study, the date, and the final evaluation must be documented in the study materials.

5. Data management and statistical analysis plan, information

confidentiality plan

A clinical trial summary report will be written based on the statistical analysis report. The investigator maintains all study materials, including confirmation of all participating subjects (able to effectively verify different recorded information, such as original hospital records), all original informed consent forms signed by the patient, and all case observation forms. The investigator will keep the information about the subjects closely until its final destruction, during which time it will not continue to use or disclose the information.

Evaluation of the Safety and Efficacy of Catheter Ablation Following Left Atrial Appendage Occlusion Using the WATCHMAN FLX Device
However, in the rare cases listed below, the investigator will continue to use or disclose information about a subject even if the subject has withdrawn from the study or the study has been completed. These situations include: when the removal of the subject's information would affect the scientific validity of the results of the study or the evaluation of the safety of the data; to provide some limited information for research, teaching, or other activities (this information will not include names, identification numbers, or other personally identifiable information); when government regulators need to oversee the study, they will ask to see all of the information about the study, which will also include information about the subject's information about their participation in the study at that time.

6. Statistical analysis

6.1 Sample size calculation

The sample size was calculated based on the primary endpoint. The primary endpoint of this study was “12-month rate of complete closure of the block after WATCHMAN FLX LAAO (CT assessment)”.

Assuming that P_0 is the target incidence rate and P_1 is the trial incidence rate, P_0 was set to 74.3% (95% confidence interval: 65.9%~ 82.7%) based on the literature reports* and expert recommendations, the hypothesis testing was as follows:

$$H_0: P_1 \leq 0.743$$

$$H_1: P_1 > 0.743$$

A P_1 of 84.3% was set, significance level $\alpha = 0.05$ (one-sided), and test efficacy $1 - \beta = 80\%$. According to the sample size formula, 200 patients were needed in a single group to fulfill the statistical requirements. Considering a 5% loss-to-follow-up rate, the total sample size was set at 210 cases.

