19	BMI	Body Mass Index
20	LAAO	Left Atrial Appendage Occlusion

Summary of the Trial Protocol

Test Name	Evaluation of the Safety and Efficacy of Catheter Ablation After Left Atrial Appendage Occlusion with the WATCHMAN FLX Device
Sponsor	Department of Cardiology, Affiliated Hospital of Nantong University
Principal Investigator	[name]
Purpose of the test	
1. Main Purpose: To evaluate the safety and efficacy of catheter ablation performed one month after WATCHMAN FLX left atrial appendage occlusion (LAAO) in patients with non-valvular atrial fibrillation(AF).
 
2. Secondary Purpose: To investigate the impact of a two-surgery sequential treatment regimen on the recurrence rate of atrial fibrillation, the incidence of stroke, and the quality of life of patients, and to provide evidence-based support for decision-making in the clinical application of combined therapy.

Trial Population	Patients diagnosed with non-valvular AF who are scheduled to undergo sequential LAAO using the WATCHMAN FLX device and catheter-based ablation.
Trial Design	
This study is a prospective, single-arm, multicenter clinical trial designed to evaluate the safety and efficacy of catheter ablation performed one month after LAAO with the WATCHMAN FLX device. Approximately 210 patients with non-valvular AF who meet the indications for both transcatheter LAAO and catheter ablation will be enrolled across 10 research centers in China. The study procedures are outlined as follows: :
 
 Patient Screening and Enrollment: Eligible patients will undergo elective LAAO with the WATCHMAN FLX device (first procedure) after signing the informed consent form (ICF). Postoperative Management: Following the LAAO with the WATCHMAN FLX device, patients will undergo standard anticoagulation therapy for one month. If transesophageal echocardiography (TEE) reveals no device-related thrombosis (DRT) or residual flow >5 mm, the patient will undergo catheter ablation for atrial fibrillation (second procedure) one month after the initial LAAO.

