	
4. Quality of life improvement at 12 months measured by the Atrial Fibrillation Effect on Quality-of-Life (AFEQT) questionnaire: Improvement in quality-of-life score from baseline to 12 months following index ablation or AAD treatment, with a possible score range of 20 to 140 (higher scores indicate worse outcomes).

Entry Criteria	
 1) Age ≥ 18 years with a diagnosis of nonvalvular AF; 2) Eligible for indications for treatment with WATCHMAN FLX LAAO and transcatheter atrial fibrillation ablation; 3) Preoperative imaging evaluation showed that the LAA anatomy was suitable for WATCHMAN FLX device implantation; 4) Patients agreed to participate in the study and signed an ICF.
Exclusion criteria	
Patients meeting any of the following criteria were not eligible for this study:
 
 1) Presence of valvular heart disease or other structural heart disease that causes atrial fibrillation; 2) Preoperative detection of LAA thrombus or acute thrombotic event; 3) The patient has a severe bleeding tendency or a recent major bleeding event (e.g. gastrointestinal hemorrhage, cerebral hemorrhage, etc.); 4) Patients who are unable to complete postoperative follow-up (e.g. life expectancy less than 1 year or poor compliance); 5) Other serious diseases (e.g. liver and kidney failure, active infections, etc.) detected on preoperative examination; 6) Women who are pregnant or breastfeeding.
statistical analysis	
1. Sample size calculation:
 
The sample size was calculated based on the primary endpoint. The primary endpoint of this study was “12-month rate of complete closure of the block after WATCHMAN FLX LAAO (CT assessment).” Hypothesized target incidence $P_0 = 74.3\%$ and test incidence $P_1 = 84.3\%$. The significance level $\alpha = 0.05$ (one-sided) and test efficacy $1 - \beta = 80\%$ were calculated to be 200 cases able to fulfill the hypothesis test. Considering the 5% shedding rate, the total sample size was 210 cases.
 
2. Descriptive Statistics:
 
Patient baseline characteristics (e.g. age, sex, history of AF) were expressed as mean \pm standard deviation or median (quartiles) for continuous variables,

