	
and frequency and percentage for categorical variables.
 
3. Primary endpoint analysis:
 
The 12-month complete closure rate of the WATCHMAN FLX device was characterized by point estimates and their 95% confidence intervals and tested against the target value of $P_0 = 74.3\%$ in a one-sample hypothesis test ($\alpha = 0.05$).
 
4. Secondary endpoint analysis:
 
Safety events (e.g. pericardial effusion, puncture site complications) were described by incidence rates and their 95% confidence intervals were calculated. Changes in quality of life were analyzed by chi-square test or paired t-test for time effects.

--	---

Text of the Trial Protocol

1. Study information

Name of Sponsor: Affiliated Hospital of Nantong University

Principal Investigator: [name]

2. Background

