6.2.2 Data analysis

Descriptive Statistics:

Patient baseline characteristics (e.g. age, sex, history of atrial fibrillation) were expressed as mean± standard deviation or median (quartiles) for continuous variables, and frequency and percentage for categorical variables.

Primary endpoint analysis:

Analyses of the primary endpoints will be performed based on mITT, with the 12-month complete closure rate of the WATCHMAN FLX device described by point estimates and their 95% confidence intervals, and a one-proportional hypothesis test ($\alpha = 0.05$) against a target value of $P_0 = 74.3\%$.

Secondary endpoint analysis:

Safety events (e.g. pericardial effusion, puncture site complications) were described by incidence rates and their 95% confidence intervals were calculated. Changes in quality of life were analyzed by chi-square test or paired t-test for time effects.

7. Ethical requirements and informed consent form

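### The stated 200 patients and 80% power do not match for the planned one-sample test: about 106 give 80%, and 200 give about 96%

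*Protocol*

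**What the plan says.** The design is a single arm: "This study is a prospective, single-arm, multicenter clinical trial". Section 6.1 of the protocol fixes every input to the sample size:

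- target rate: "P_0 was set to 74.3% (95% confidence interval: 65.9%~ 82.7"%), entered in the hypotheses as the constant 0.743
- expected rate: "A P_1 of 84.3% was set"
- error rate: "significance level $\alpha = 0.05$ (one-sided")
- power: 80%

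It then states the result: "According to the sample size formula, 200 patients were needed in a single group to fulfill the statistical requirements". Allowing for 5% loss to follow-up, the total becomes 210. The summary (statistical analysis, item 1) repeats this, with the size "calculated to be 200 cases able to fulfill the hypothesis test".

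The planned primary analysis is a test against the fixed 74.3%. The summary (item 3) describes it as "in a one-sample hypothesis test", and Section 6.2.2 as "a one-proportional hypothesis test". The protocol does not name the sample-size formula and gives no reason for 200 other than the power requirement.

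**The concern.** With all inputs stated, the result can be checked directly. A 10-point difference from a fixed target of 74.3%, at one-sided 0.05 and 80% power, should need far fewer than 200 patients. A comparison of two estimated proportions, by contrast, would need a number of that order in each group.

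If 200 comes from a two-group formula, the protocol misstates the power of its own primary test, and the justification for enrolling 210 patients, each scheduled for two invasive procedures, does not follow from the planned analysis. A reader who recomputes the size cannot tell whether the number, the power or the test is wrong.

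**Working it through.** **Inputs** (Section 6.1): P0 = 0.743, P1 = 0.843, difference 0.10, one-sided alpha 0.05 (z = 1.645), power 80% (z = 0.8416).

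Variances: P0(1 − P0) = 0.190951, root 0.43698. P1(1 − P1) = 0.132351, root 0.36380.

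**1. Reproducing the stated 200.** The formula for two independent proportions, unpooled, per group, is

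n = (z_α + z_β)² × [P0(1 − P0) + P1(1 − P1)] / (P1 − P0)²

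= 6.1826 × 0.323302 / 0.01 = 199.88, rounded up to **200 per group**.

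The pooled form gives 202. The figure therefore appears when 74.3% is treated as the estimated rate of a second arm, which this trial does not have. The step to 210 is 200 × 1.05. Dividing by 0.95 gives 210.5, so 211, a negligible difference.

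**2. The formula that fits the planned test.** For one sample against a fixed value,

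n = [(z_α √(P0(1 − P0)) + z_β √(P1(1 − P1))) / (P1 − P0)]²

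= [(1.645 × 0.43698 + 0.8416 × 0.36380) / 0.10]² = [(0.7188 + 0.3062) / 0.10]² = 105.05, rounded up to **106**.

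**3. Exact binomial.** At one-sided 0.05, 80% power is first reached at n = 104 (power 80.6%). Exact power is not monotone in n: it is 78.1% at n = 106, and it is at or above 80% for every n from **118**.

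**4. With 5% loss.** 106 / 0.95 = 111.6, so 112. 118 / 0.95 = 124.2, so 125. The protocol has 210.

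**5. Power at n = 200.**

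- Exact: the smallest critical value with size at most 0.05 is 160 successes. P(X ≥ 160 | 0.743) = 0.0363 and P(X ≥ 160 | 0.843) = **0.958**.
- Normal approximation: Φ((0.10 × √200 − 1.645 × 0.43698) / 0.36380) = Φ(1.912) = **0.972**.

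**6. Rate detectable at n = 200.** P(X ≥ 160 | 0.8202) = 0.80, so 80% exact power applies at a true rate of about 82.0%. The normal approximation gives about 81.7%.

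**7. Could another one-sample calculation give 200?** On the stated alpha and power:

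| One-sample form | n | With continuity correction |
|---|---|---|
| Both variances (step 2) | 106 | 115 |
| P0 variance only | 119 | 128 |
| P1 variance only | 82 | 92 |
| Arcsine | 101 | 110 |

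Changing the inputs in the step 2 formula gives 136 (two-sided 0.05), 141 (90% power) and 175 (both). The P0-only form with both changes gives 200.6, so 201, but the protocol states neither two-sided alpha nor 90% power.

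**The case against.** **The error does little harm.** The trial is larger than its stated power requires, not smaller. Type I error, the estimate and its interval are untouched, and the conclusion on the primary endpoint does not depend on the stated power. This stands and limits the weight of the point. It does not make the statement correct: the protocol says 200 were needed for 80% power, and they were not.

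**The origin is not proven.** The two-group formula is not the only route to about 200, since a one-sample form using only the P0 variance gives 201 with two-sided 0.05 and 90% power. This also stands, and the two-group origin should be read as an inference. That alternative contradicts the stated sidedness and power, however, so it does not support the figure. The mismatch holds whatever the origin.

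**The sidedness of the analysis is not restated.** The summary (item 3) and Section 6.2.2 give alpha 0.05 beside a 95% confidence interval and do not say one-sided. If the test were two-sided, power at 200 would be 93.9% exact or 93.7% by normal approximation. Section 6.1 does specify one-sided, and either reading is far from 80%.

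**The two headline figures come from different methods.** The 106 is a normal-approximation figure and the 96% is exact; exact power at 106 is 78.1%. That is a fair caution for the replacement text, which should pair 106 with 97.2%, or 104 to 118 with 95.8%.

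**Conclusion.** The concern holds. On the protocol's own inputs, 80% power needs 106 evaluable patients by normal approximation, or 104 to 118 by the exact binomial test. The stated 200 is about 1.9 times the 106 (200 / 106 = 1.89). With 200 evaluable patients the one-sided test has 95.8% power (exact) or 97.2% (normal approximation), against 80% stated.

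This rests on the target being a fixed constant, as the hypotheses in Section 6.1 set it, on a one-sided test at 0.05, and on all 200 patients being evaluable for the primary endpoint. It does not depend on how the 200 was obtained. It should be corrected, but it is an error in the justification and does not threaten the validity of the primary result.

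**What to change.** In Section 6.1 and in the summary (statistical analysis, item 1), name the one-sample method, keep 200 evaluable and 210 enrolled, and state the power they provide, using one method throughout. For example:

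> For a one-sample exact binomial test at one-sided alpha 0.05 of a target rate of 74.3%, with an expected rate of 84.3%, 80% power is maintained from 118 evaluable patients. The trial plans 200 evaluable patients (210 allowing for 5% loss), which gives about 96% power at 84.3%, or 80% power at a true rate of about 82%.

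If the normal approximation is preferred, the matching figures are 106 patients for 80% power and about 97% power at 200.

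The sponsor should then add its own reason for the larger size. Precision of the safety rates would be one possible reason: with no event observed, the one-sided 95% upper limit is 1 − 0.05^(1/200) = 1.5% at 200 patients, against 1 − 0.05^(1/106) = 2.8% at 106. Only the sponsor can say whether that was the intention.

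The cost is a few sentences in two places. The number of patients, the alpha and the test do not change.
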